### 13.3. Objectives, Endpoints, and Estimands for Sub-Study B

The following objectives and endpoints are specific to the Sub-Study B:

**Table 24. Sub-Study B Objectives and Endpoints**

Objectives	Endpoints
Primary:	Primary:
Phase 1b	Phase 1b

 
To assess the DLT rate and estimate the MTD of sasanlimab in combination with axitinib and SEA-TGT to determine the RP2D for the combination.
 
	
 
DLTs during the DLT-observation period.
 

Phase 2	Phase 2

 
To assess the ORR of sasanlimab in combination with axitinib and SEA-TGT.
 
	
 
OR, defined as confirmed CR or PR, as assessed by the investigator using RECIST v1.1.
 

Secondary:	Secondary:
Phase 1b	Phase 1b

 
To assess the overall safety and tolerability of the combined investigational products.
 
	
 
AEs graded according to the NCI-CTCAE v5.0 and changes in clinical laboratory test parameters.
 

 
To assess the anti-tumor activity of the combined investigational products.
 
	
 
OR, DR, TTR, PFS by investigator assessment using RECIST v1.1.
 

 
To characterize the PK of the investigational products.
 
	
 
PK parameters (<math>C_{max}</math>, <math>C_{trough}</math>) of sasanlimab, axitinib, and SEA-TGT, as data permit.
 

**Table 24. Sub-Study B Objectives and Endpoints**

Objectives	Endpoints

 
To evaluate the immunogenicity of sasanlimab.
 
	
 
ADA (ie, incidence) against sasanlimab, as data permit.
 

 
To evaluate the immunogenicity of SEA-TGT.
 
	
 
ADA (ie, incidence) against SEA-TGT, as data permit.
 

Phase 2	Phase 2

 
To assess other measures of anti-tumor activity of the combined investigational products.
 
	
 
DR, TTR, PFS by investigator assessment using RECIST v1.1, and OS.
 

 
To assess the overall safety and tolerability of the combined investigational products.
 
	
 
AEs graded according to the NCI-CTCAE v5.0 and changes in clinical laboratory test parameters.
 

 
To characterize the PK of the investigational products.
 
	
 
PK parameters (<math>C_{max}</math>, <math>C_{trough}</math>) of sasanlimab, axitinib, and SEA-TGT, as data permit.
 

 
To evaluate the immunogenicity of sasanlimab.
 
	
 
ADA against sasanlimab, as data permit.
 

 
To evaluate the immunogenicity of SEA-TGT.
 
	
 
ADA against SEA-TGT, as data permit.
 

 
To assess the association between anti-tumor activity and PD-L1 expression.
 
	
 
OR by PD-L1 expression in available tumor tissue (archival or de novo, primary or metastatic).
 

Exploratory	Exploratory
Phase 1b	Phase 1b

 
To understand the relationship between the therapeutic interventions being studied and the biology of the participant's NSCLC.
 
	
 
Biomarkers, consisting of DNA, RNA, protein, metabolites or defined cell types, resulting from analyses of peripheral blood and/or tumor tissue biospecimen obtained at baseline, on treatment or at end-of-study.
 

Phase 2	Phase 2

 
To understand the relationship between the therapeutic interventions being studied and the biology of the participant's NSCLC.
 
	
 
Biomarkers, consisting of DNA, RNA, protein, metabolites or defined cell types, resulting from analyses of peripheral blood and/or
 

**Table 24. Sub-Study B Objectives and Endpoints**

Objectives	Endpoints
	tumor tissue biospecimen obtained at baseline, on treatment or at end-of-study.

### **Estimands**

This section defines the estimands associated with the primary endpoints of the sub-study.

The primary endpoint definitions and the observations that will be considered in the derivation of the endpoints are described or referenced below.

#### **Phase 1b:**

Primary Estimand (DLT): DLT rate estimated based on data from DLT-evaluable participants during the DLT-evaluation period (Cycle 1 – first 21 days of study treatment) in Phase 1b.

Variable: Occurrence of DLTs.

Analysis population: DLT-evaluable participants defined as participants who receive at least 1 dose of the combination study treatment in Phase 1b and either experience DLT during the DLT-evaluation period or complete the DLT-evaluation period without DLT. Participants without DLTs who receive less than 75% of the planned dose of each study intervention in Cycle 1 for reasons other than treatment-related toxicity are not evaluable for DLT. All participants deemed non-evaluable for DLT may be replaced.

Population-level summary measure: DLT rate defined as the number of DLT-evaluable participants with DLTs in the DLT-evaluation period divided by the number of DLT-evaluable participants in the DLT-evaluation period.

#### **Phase 2:**

Primary Estimand (OR): the treatment effect of sasanlimab + axitinib + SEA-TGT assessed by the ORR, based on Investigator assessment per RECIST v1.1, in the analysis population.

- Variable: Objective response defined as confirmed CR or PR according to RECIST v1.1 based on investigator assessment. Both CR and PR must be confirmed by repeat assessments performed no less than 4 weeks after the criteria for response are first met.
- Analysis population: all participants who received at least 1 dose of study intervention without regard to tolerability or duration of treatment.

[figure not shown]
- Population-level summary measure: ORR is defined as the proportion of participants in the analysis population with an OR and 2-sided 95% CI for ORR using the Clopper-Pearson method. Participants who do not have a post-baseline tumor assessment due to early progression of disease, who receive anti-cancer therapies other than the study treatments prior to reaching a CR or PR, or who die, or have PD, or stop tumor assessments for any reason prior to reaching a CR or PR will be counted as non-responders in the assessment of OR. Each participant will have an objective response status (0: no OR; 1: OR).

### 13.4. Study Design for Sub-Study B

See [Section 4.1](#) for the overall study design in the master protocol.

Figure 3 illustrates the design of Sub-Study B. Sub-Study B will start with a Phase 1b dose-finding safety part to identify the RP2D for the triplet combination of sasanlimab +axitinib + SEA-TGT. Approximately 20 participants with any line of previous therapy will be enrolled in Phase 1b. Phase 2 will evaluate the anti-tumor activity and additional safety of the triplet combination in approximately 60 participants in the 1L or 2L/3L who have progressed on or after prior PDx treatment. The sasanlimab dose of **CCI** will remain fixed for all cohorts in Phase 1b and Phase 2 of Sub-Study B. Doses of axitinib and SEA-TGT will be identified via the mTPI dose-finding design. See [Sections 13.4.1](#) and [13.4.2](#) for more details on the study design of Phase 1b and Phase 2, respectively.

**Figure 3. Sub-Study B Design**

### 13.4.1. Phase 1b Design

Phase 1b will enroll participants in any line therapy for advanced NSCLC with no restrictions on the types of previous therapies, and who have any PD-L1 expression status. First, the safety of the sasanlimab and axitinib combination will be confirmed. Up to 2 dose levels of axitinib given in combination with sasanlimab CCI will be investigated (Table 25). The decision to de-escalate (from 5 mg BID to 3 mg BID) will be based on mTPI decision criteria based on the number of DLT evaluable patients and number of DLTs in those participants.

Initially 3-4 participants will be treated with sasanlimab CCI axitinib 5 mg BID and monitored during the 21-day DLT evaluation period (Cycle 1). If the mTPI decision criteria allows escalation, then the triplet cohort may be opened. Otherwise, the doublet cohort can be expanded with an additional 3 patients enrolled or de-escalated to the lower dose (3 mg BID) per the mTPI decision criteria.

**Table 25. Sub-Study B Phase 1b, Doublet Cohorts Dose Levels**

Dose Level	Sasanlimab	Axitinib
0 (Starting Dose)	CCI	5 mg BID
-1	CCI	3 mg BID

DLT period = 1 cycle of 21 days.  
 mTPI dose finding schema will be used for dose finding.

After the safety of the doublet is confirmed, the triplet combination may be opened. Up to three dose levels of SEA-TGT may be investigated (Table 26) and initially 3-4 participants will be treated and monitored at the starting dose level. The enrollment of subsequent participants (dose escalation or de-escalation cohorts) will be guided by mTPI design. At least 6 patients will be treated at the RP2D of the triplet combination before proceeding to Phase 2.

**Table 26. Sub-Study B, Phase 1b, Triplet Cohorts Dose Levels**

Dose Level	Sasanlimab	Axitinib*	SEA-TGT
1	CCI	3 or 5 mg BID	3 mg/kg IV Q3W
0 (Starting Dose)	CCI	3 or 5 mg BID	1 mg/kg IV Q3W
-1	CCI	3 or 5 mg BID	0.3 mg/kg IV Q3W

DLT period = 1 cycle of 21 days.  
 mTPI dose finding schema will be used for dose finding.  
 \*Axitinib dose will be determined by the doublet cohorts and will be fixed in the triplet cohorts.

A minimum of 3 DLT-evaluable participants will be required in each cohort; additional participants will be enrolled in the specific enrollment cohort to replace participants who are not considered DLT-evaluable, where required. When all DLT-evaluable participants treated in a given enrollment cohort have completed the DLT observation period or experienced a DLT, whichever occurs first, the posterior probabilities for the risk of DLT for new

participants at different dose levels for the combination of interest will be evaluated. If the toxicity rate of the currently used dose level is far smaller than the target probability of toxicity (pT) of 0.30, the mTPI will recommend escalating the dose level; if it is close to pT, the mTPI will recommend continuing at the current dose; if it is far greater than pT, the mTPI will recommend de-escalating the dose level. The mTPI dose de-escalation/escalation recommendation will be based on the estimated toxicity rate and 3 intervals (underdosing, target toxicity, and excessive toxicity) as shown below:

- If current dose is in the underdosing [0, 0.25) toxicity interval: escalate to next higher dose;
- If current dose is in the target toxicity [0.25, 0.35) toxicity interval: stay at current dose;
- If current dose is in the excessive toxicity or overdosing [0.35, 1] toxicity interval: de-escalate to a lower dose

Refer to [Section 13.9](#) and [Section 13.10.6](#) for more details on the mTPI design and decision rules.

The number of participants to be enrolled in Phase 1b will depend upon the observed safety profile, which will determine the number of participants at each dose level and the number of dose levels explored.

It is anticipated that up to approximately 20 total participants will be enrolled in Phase 1b starting with Dose Level 0 of the doublet cohorts, and including the triplet cohorts.

An RP2D below the MTD, or highest safe dose tested, may be determined based on other safety, clinical activity, PK, and pharmacodynamic data.

Cumulative DLT data will continue to be evaluated using the mTPI design in the Phase 2 part. Should emerging data indicate that the dose level tested in the Phase 2 expansion cohort is more toxic than previously estimated ( $\geq 35\%$  DLT rate), the next lower dose level may be explored, and may be declared as the RP2D for the triplet combination.

#### **13.4.2. Phase 2 Design**

Once the RP2D of the triplet is defined, the Phase 2 part of the study may be initiated. Patients will be allocated to 1 of 3 treatment arms based on lines of prior therapy and PD-L1 TPS. For participants with previously untreated NSCLC, competitor data for PDx/TIGIT doublet combinations suggest that clinical activity may be enriched in the subgroup of patients with PD-L1 TPS  $\geq 50\%$  as compared to those with PD-L1 TPS 1-49%. Therefore, participants will be enrolled into 2 separate treatment arms based on PD-L1 expression to allow for estimation of clinical activity in each subgroup:

- Treatment Arm B1 (n=20): treatment-naïve participants with low PD-L1 (levels 1-49%);

- Treatment Arm B2 (n=20): treatment-naïve participants with high PD-L1 (levels  $\geq 50\%$ ).

Given the existing data and high unmet need, a 3rd group of patients who have received prior checkpoint treatment is planned:

- Treatment Arm B3 (n=20): patients whose disease has progressed on prior PD-1/PD-L1 therapy and who have PD-L1 TPS  $\geq 1\%$ .

Phase 2 will enroll a total of approximately 60 participants and will evaluate the anti-tumor activity and further evaluate the safety of the triplet combination of sasanlimab + axitinib + SEA-TGT.

### 13.4.3. Rationale for the Sub-Study B Combination

See [Section 2.1](#) for the overall study rationale in the master protocol.

Despite advances in the treatment landscape for patients with advanced NSCLC, progression-free survival (PFS) remains modest. While the introduction of PD-1/PD-L1 inhibitors improved clinical outcomes compared to chemotherapy, not all patients benefit from single-agent PD-1/PD-L1 inhibitors.

Recent data for PD-1/PD-L1 inhibitors combined with anti-TIGIT have demonstrated improvement in clinical outcomes over single-agent PD-1/PD-L1 inhibitors in patients with advanced NSCLC, regardless of PD-L1 status:

- CITYSCAPE (NCT03563716), a randomized double-blind, Phase 2 study in advanced NSCLC (N=67; TPS  $\geq 1\%$ ) indicated that the addition of anti-TIGIT tiragolumab to atezolizumab resulted in superior ORR & PFS versus atezolizumab + placebo:
  - ORR was 31% vs 16% in the tiragolumab + atezolizumab arm vs placebo + atezolizumab arm. Odds Ratio=2.57 (1.07, 6.14).
  - Median PFS was 5.4 months in the tiragolumab + atezolizumab arm vs 3.6 months in the placebo + atezolizumab arm. HR= 0.57 (0.37, 0.90).
  - A greater magnitude of improvement was seen in the TPS  $\geq 50\%$  group.
- Vibostolimab combined with pembrolizumab in patients with NSCLC whose disease progressed on prior PDx therapy (n=38): ORR was 5% (95% CI: <1, 18) and median duration of response was 13 months (95% CI: 4, 13).
- Vibostolimab combined with pembrolizumab in patients with PDx-naïve NSCLC, (n=41; both TPS  $\geq 1\%$  and  $<1\%$ ): ORR was 29% (95% CI: 16, 46) and median PFS was 5.4 months (95% CI: 2.1, 8.2); median duration of response was not reached.

In addition to inhibition of PD-1/PD-L1 and TIGIT, VEGF pathway inhibition may make the tumor microenvironment more responsive. Successfully targeting these non-overlapping mechanisms may lead to additive or synergistic activity. Single-agent axitinib has

demonstrated antitumor activity in patients with advanced NSCLC who have either received prior therapy or not (see [Section 13.2.2.3.1](#)).

The VEGF pathway has been linked with tumor immunosuppression. Elevated expression of genes characteristic of angiogenesis has been associated with reduced OS benefit from avelumab in patients who otherwise show elevated immune activity in tumor. These findings are consistent with the hypothesis that inhibition of the VEGF pathway in conjunction with PD-1/PD-L1 inhibitors will improve patient benefit. This hypothesis has been supported by the clinical studies reported below. Clinical benefit from the combination of avelumab + axitinib in renal cancer and from maintenance avelumab following chemotherapy in advanced urothelial carcinoma is associated with elevated TIGIT expression. TIGIT may therefore limit clinical benefit in the context of anti-tumor immunity enabled by VEGF pathway and PD(L)1 inhibition. The addition of a TIGIT antagonist in such a setting is expected to further improve clinical benefit.

Combinations of PD-1/PD-L1 inhibitors + VEGFR inhibitors (without anti-TIGIT) have demonstrated clinical proof of concept with acceptable safety profiles in several malignancies, including advanced NSCLC:

- Avelumab + axitinib (n=41; PDx naïve advanced NSCLC): ORR=32% (95% CI: 18.1, 48.1). Clinical activity in this population was not associated with PD-L1 expression. Avelumab + axitinib combination responders were associated with an activated immune profile, including the TIGIT pathway.
- Cabozantinib + atezolizumab (n=30; advanced NSCLC patients previously treated with an ICI, 2L setting): ORR of 27% (80% CI: 16, 40).
- Lenvatinib + pembrolizumab: (n=21; 11[52%] received prior ICI, advanced NSCLC): ORR=33% (95% CI: 14.6, 57.0). This combination demonstrated a manageable safety profile and promising antitumor activity in patients with selected solid tumors.

#### 13.4.4. Justification for Dose in Sub-Study B

##### 13.4.4.1. Starting Dose for Phase 1b

The starting dose of sasanlimab in Sub-Study B is **CCI** and will remain constant throughout the study. Refer to master protocol [Section 4.3](#) for the justification for this starting dose.

The axitinib dose of 5 mg orally twice daily, with or without food, was selected for the starting dose to test dose limiting toxicity in combination with sasanlimab and SEA-TGT. The 5 mg BID dose has proven to be safe and efficacious as a single agent and in combination with checkpoint inhibitors for the treatment of patients with aRCC. It is the dose approved by regulatory authorities worldwide.

The SEA-TGT starting dose was chosen based on PK and PD data in the ongoing first-in-human study SGNTGT-001, in the absence of an MTD. Single-agent doses explored in that study were 0.01, 0.1, 0.3, 1, 3, and 6 mg/kg; SEA-TGT monotherapy demonstrated acceptable safety and tolerability at all dose levels evaluated ([Section 13.2.2.3.2](#)). The data

showed strong biologic activity at the lowest dose tested (0.01 mg/kg), sustained target engagement and linear PK were observed starting at 0.3 mg/kg, and minimal PD differences were observed between 1 and 3 mg/kg. Based on these data and the DLT event at 6 mg/kg (Grade 3 pruritic rash), no further dose escalation will occur. Therefore the 1 and 3 mg/kg doses were recommended for further development.

#### **13.4.4.2. Criteria for Dose Escalation/De-Escalation**

Refer to [Section 13.10.6](#) for criteria for dose escalation/de-escalation via mTPI for Sub-Study B.

#### **13.4.5. Dose Limiting Toxicity**

Refer to master protocol [Section 4.3.3](#) for the definition of DLT.

The DLT observation period is the first 21 days starting with the first dose of any study intervention in the combination.

#### **13.4.6. Maximum Tolerated Dose**

The MTD is the highest studied dose level associated with a DLT rate of <35% among the participants treated at that dose level following the mTPI method.

#### **13.4.7. Recommended Phase 2 Dose (RP2D) Definition**

Refer to master protocol [Section 4.3.5](#).

### **13.5. Study Population for Sub-Study B**

**Participants must meet all of the general inclusion and exclusion criteria as specified in the master protocol ([Section 5](#)) plus the following Sub-Study B specific inclusion and exclusion criteria:**

#### **13.5.1. Inclusion Criteria for Sub-Study B**

##### **Phase 1b and Phase 2:**

14. Urinary protein <2+ by urine dipstick. If dipstick is  $\geq 2+$ , then a 24-hour urinary protein <2g per 24 hours.
15. Baseline blood pressure readings of  $\leq 150$  mm Hg (systolic) and  $\leq 90$  mm Hg (diastolic), as documented by 2 blood pressure readings taken at least 1 hour apart.
16. Left ventricular ejection fraction (LVEF)  $\geq$  lower limit of normal as assessed by either MUGA scan or ECHO.

##### **Phase 1b only:**

17. Any line of therapy for locally advanced/metastatic NSCLC.

**Phase 2 only:**

18. Able to provide a sufficient amount of plasma and tumor (primary or metastatic, archival or newly obtained); approximately 15 slides (minimum of 10 slides) or block are required for central lab determination of PD-L1 tumor expression and exploratory analyses. If archived tissue is not available and a fresh tumor biopsy is not considered appropriate in the opinion of the investigator, discussion with the sponsor is required.

**Phase 2 Arms B1 and B2 (1st Line) only:**

19. Previously untreated for advanced/metastatic NSCLC.
20. PD-L1 TPS 1%-49% (Arm B1) or  $\geq 50\%$  (Arm B2), as determined by local lab assay.

**Phase 2 Arm B3 (2nd/3rd Line) only:**

21. One or 2 prior lines of therapy for advanced/metastatic NSCLC.
  - Must have received prior immune checkpoint inhibitor treatment (at least anti-PD-1/PD-L1 directed therapy) and platinum-based doublet chemotherapy, sequentially or concomitantly, and have documented disease progression while or after receiving the therapy.
22. PD-L1 TPS  $\geq 1\%$  as determined by local laboratory assay.

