##### **Type of Participant and Disease Characteristics:**

6. Documented histologically or cytologically confirmed locally advanced/metastatic (Stage IIIB-IV) NSCLC, per AJCC/ International Union for Cancer Control TNM system, 7th edition. For Stage IIIB disease relapse during treatment or within 6 months following adjuvant therapy will be considered metastatic disease. In addition, for Stage IIIB, must not be amenable for definitive therapy (eg, surgery or chemoradiation).
7. At least 1 measurable lesion per RECIST v1.1 at Screening.
8. ECOG Performance Status 0 or 1.
9. Resolved acute effects of any prior therapy to baseline severity or CTCAE Grade  $\leq 1$ , unless otherwise specified.
10. Life expectancy  $\geq 3$  months as assessed by the investigator for previously treated participants or  $\geq 12$  months for first-line untreated participants.

11. Adequate bone marrow function (without hematopoietic growth factor or transfusion support within 14 days prior to first dose of study intervention), including:

- a. Absolute neutrophil count  $\geq 1500/\text{mm}^3$  or  $\geq 1.5 \times 10^9/\text{L}$ ;
- b. Platelets  $\geq 100,000/\text{mm}^3$  or  $\geq 100 \times 10^9/\text{L}$ ;
- c. Hemoglobin  $\geq 9$  g/dL (may have been transfused).

12. Adequate renal function, defined by:

Estimated creatinine clearance  $\geq 30$  mL/min according to the Cockcroft-Gault formula or by 24-hour urine collection for creatinine clearance, or according to local institutional standard method.

13. Adequate liver function, including:

- a. Total serum bilirubin  $\leq 1.5 \times \text{ULN}$  unless the participant has documented Gilbert syndrome;
- b. AST and ALT  $\leq 2.5 \times \text{ULN}$ ;  $\leq 5.0 \times \text{ULN}$  if there is liver involvement by the tumor;
- c. Alkaline phosphatase  $\leq 2.5 \times \text{ULN}$  ( $\leq 5 \times \text{ULN}$  in case of bone metastasis).

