**Prior/Concomitant Therapy:**

14. Live attenuated vaccines within 4 weeks prior to first dose of study intervention and while on study treatment.
15. Major surgery or received radiation therapy within 2 weeks prior to first dose of study intervention.

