### 12.5.2. Exclusion Criteria for Sub-Study A

#### Phase 1b only:

17. Receipt of anticancer medications or investigational drugs within the following intervals before the first dose of study intervention:

- a. ≤14 days for chemotherapy, targeted small-molecule therapy, radiation therapy, or antineoplastic biologic therapy.
- b. ≤14 days or 5 half-lives (minimum of 14 days) for investigational agents or devices. For monoclonal antibodies, <28 days from the last dose.

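### Sub-Study B sets no minimum interval from prior systemic anticancer or investigational drugs, so one misattributed event can change a Phase 1b dose decision

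*Protocol*

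**What the plan says.** Sub-Study B has two pretreated populations.

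- **Phase 1b.** Section 13.4.1 says "Phase 1b will enroll participants in any line therapy for advanced NSCLC with no restrictions on the types of previous therapies". Inclusion criterion 17 in Section 13.5.1 repeats it as "Any line of therapy for locally advanced/metastatic NSCLC", with no time limit.
- **Phase 2 Arm B3.** Inclusion criterion 21 requires one or two prior lines and reads "Must have received prior immune checkpoint inhibitor treatment (at least anti-PD-1/PD-L1 directed therapy) and platinum-based doublet chemotherapy, sequentially or concomitantly". It goes on to require that participants "have documented disease progression while or after receiving the therapy".

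Sub-Study A, whose Phase 1b is also open to any line, has an exclusion (criterion 17, Section 12.5.2) for "Receipt of anticancer medications or investigational drugs within the following intervals before the first dose of study intervention", followed by a list of intervals by type of drug.

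The master protocol (Section 5.2) has a time-based rule of this kind only for live vaccines and for "Major surgery or received radiation therapy within 2 weeks prior to first dose of study intervention". Master inclusion 9 asks for "Resolved acute effects of any prior therapy to baseline severity or CTCAE Grade" 1 or lower, which concerns severity and not time.

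**The concern.** Phase 1b dose finding rests on toxicities in the first 21 days that are attributed to study drug, in cohorts of three or four. If a participant stopped another checkpoint inhibitor, or an anti-TIGIT or anti-VEGF drug, shortly before Cycle 1 Day 1, a hepatic or immune event in that window has two plausible sources. Section 13.2.3 itself lists hepatotoxicity, hypothyroidism and diarrhea among the events that may overlap for axitinib with sasanlimab, and expects some overlap of immune-related events between sasanlimab and SEA-TGT.

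The error can run either way. A late effect of the earlier drug may be counted as a DLT, or a true DLT may be put down to the earlier drug. What is at stake is the recommended Phase 2 dose, which all of the roughly 60 Phase 2 participants then receive. Section 13.4.1 also keeps DLT data under mTPI review in Phase 2, so Arm B3 can contribute to the same count.

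A second, smaller question is whether a late effect of the previous regimen could be credited to the triplet in Arm B3.

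**Working it through.** **1. Is there an interval anywhere that binds Sub-Study B?**

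- Section 13.5.2, exclusions 17 to 30: the pre-dose interval for named drug classes covers CYP3A4/5 inducers (both phases) and strong CYP3A4 inhibitors (Phase 1b). Nothing is set for anticancer or investigational drugs.
- Exclusion 27 bars prior anti-TIGIT and anti-VEGF therapy altogether, but only in Phase 2. Phase 1b participants may come directly from such drugs.
- Master Section 5.2: 4 weeks for live vaccines, 2 weeks for major surgery and radiotherapy. Systemic drugs are not covered.
- Section 6.5.1 bars other anti-tumor treatment only while study treatment is being given.
- Sub-Study A exclusion 17 sits in that sub-study's own appendix and does not carry over. Sub-Study A Phase 2 is previously untreated, so its rule covers exactly its pretreated population. Sub-Study B has no counterpart and gives no reason.

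**2. What do the existing safeguards cover?**

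- Inclusion 9: acute effects already resolved.
- Inclusions 11 and 13: marrow and liver limits at entry.
- Exclusion 2: previous Grade 3 or higher, or unresolved, immune-related events.
- Section 4.3.3: a DLT must be attributable to a study intervention.

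The first three describe the participant at entry. The fourth depends on a causality judgment between overlapping exposures. None addresses toxicity that appears after entry from a drug given shortly before it.

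**3. Size in Phase 1b.** First, reproduce the n = 3 column of Table 30. Section 13.10.6 gives a target of 0.30 and e1 = e2 = 0.05. A uniform Beta(1,1) prior and a 0.95 elimination cut-off are assumed here, since the protocol states neither. The posterior after r DLTs in n is Beta(1+r, 1+n−r). Each interval's unit probability mass is its posterior probability divided by its length (0.25, 0.10, 0.65).

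- 0/3: under (1 − 0.75⁴)/0.25 = 2.73; target (0.75⁴ − 0.65⁴)/0.10 = 1.38; over 0.65⁴/0.65 = 0.27. Escalate.
- 1/3: 1.05, 1.75, 0.87. Stay.
- 2/3: 0.20, 0.76, 1.34. De-escalate; P(rate > 0.30) = 0.916, below 0.95, so the dose is not eliminated.
- 3/3: P(rate > 0.30) = 1 − 0.3⁴ = 0.992. Eliminate.

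This matches Table 30. The same rule also matches its columns for 4 and 6.

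Effect of one misattributed event:

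- 3 treated: 0/3 Escalate to 1/3 Stay; 1/3 Stay to 2/3 De-escalate; 2/3 De-escalate to 3/3 eliminated. Every step changes the decision.
- 4 treated: 0/4 Escalate to 1/4 Stay, and 2/4 Stay to 3/4 eliminated, but 1/4 to 2/4 remains Stay.
- 6 treated: 1/6 Escalate to 2/6 Stay, and 3/6 Stay to 4/6 eliminated; 0 to 1 and 2 to 3 change nothing.

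A true DLT blamed on the earlier drug reverses each step, for example 1/3 Stay becomes 0/3 Escalate.

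Illustration only, with an assumed probability q of a carry-over event counted as a DLT, independent of the true rate t: P(escalate after 3) = [(1 − t)(1 − q)]³.

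- t = 10%: 0.729 at q = 0, 0.625 at q = 5%, 0.531 at q = 10%.
- t = 20%: 0.512, 0.439, 0.373.

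The values of q are not from the documents.

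**4. Arm B3 response.** One response in 20 is 1/20 = 5 percentage points. For example, 2/20 = 10% (95% CI 1.2 to 31.7) becomes 3/20 = 15% (3.2 to 37.9). For carry-over to occur, a participant would have to meet the progression requirement and then show a confirmed response to the earlier drug. The route is narrow but not closed: Section 10.9 allows a baseline scan up to 28 days before treatment, and nothing bars a systemic dose between that scan and Cycle 1 Day 1.

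**The case against.** The other side has real weight. Taken together, the safeguards in Sections 4.3.3, 5.1 and 5.2 go well beyond inclusion 9, the sponsor reviews eligibility before enrollment, and investigators may wait in practice. A spurious DLT pushes the design toward a lower dose, which is the cautious direction. The sub-study is exploratory, and its Phase 2 arms only estimate a response rate. An interval of the Sub-Study A kind would not remove all delayed immune toxicity from a prior antibody.

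Most of that stands as a limit on size. It does not remove the gap. Sponsor review applies the written criteria, which contain no interval. The opposite error, a true DLT attributed to the previous drug, is not cautious.

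Three stronger readings might be inferred, and the documents do not support them.

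- **That carry-over does enter both the DLT count and the Arm B3 response rate.** The text shows only that it can. For Arm B3 the progression requirement is the main safeguard; a regimen stopped for toxicity matters chiefly in the narrow case of a second line ended without progression. Section 10.9 also asks for baseline scans as close as possible to study start, and an older scan in a progressing patient can work against a response.
- **That delayed myelosuppression cannot be told apart because the study drugs share it.** The common adverse events listed for axitinib (Section 13.2.2.3.1) and SEA-TGT (Section 13.2.2.3.2) do not include neutropenia or thrombocytopenia, and Section 2.2.2 gives Grade 4 neutrophil decrease at 0.9% for sasanlimab. The overlap is credible for hepatic and immune events.
- **That one carried-over response would equal the 5% response rate cited in Section 13.4.3 for an anti-TIGIT doublet after PD-1 progression.** The arithmetic is right, but that figure comes from another combination and is no evidence that carry-over happens.

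**Conclusion.** The point holds in a limited form. Sub-Study B has no minimum interval from prior systemic anticancer or investigational therapy, Sub-Study A Phase 1b has one, and no reason for the difference is given. This is an eligibility rule, so an analysis plan could not supply it.

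The main consequence is in Phase 1b. In a cohort of three, any single misattributed event alters the dose decision; in cohorts of four or six, some do. How often this would happen cannot be drawn from the documents, and the 5% and 10% figures above are assumptions. The conclusion rests on overlap of hepatic and immune toxicity between recent prior drugs and the study drugs, and on DLT attribution being a judgment. The Arm B3 response issue is secondary. This should be fixed; it does not invalidate the design.

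**What to change.** Reconcile Section 13.5.2 with Sub-Study A exclusion 17: add, for Phase 1b and Arm B3, an exclusion for systemic anticancer and investigational drugs received within an interval before Cycle 1 Day 1. The sponsor should set the interval by type of drug and give the reason; no value is proposed here. If the sponsor means to have none, the protocol should say why Sub-Study B differs. In addition, require the Arm B3 baseline scan to be taken after the last dose of prior therapy.

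The cost is one criterion and one scan-timing rule in an amendment. Some participants would wait a short time before the first dose, and an occasional baseline scan would have to be taken later. Sample sizes, the mTPI rules and the planned analyses are unchanged.
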